5.5 Blinding

This is a double-blind study. All IP will be prepared and administered by an unblinded study staff member. Investigational product accountability will be monitored by a separate unblinded monitor. All other persons involved in the study will be blinded to study group assignment, including the study staff observing the subject after vaccination and the subject. Until the final database lock and unblinding, all unblinded data analyses will be handled by the unblinded team of statisticians and programmers. A strict firewall between the blinded and unblinded teams will be maintained.

For the 2 planned interim analyses, BARDA, site personnel, and subjects will be unblinded for all interim data at Day 43 and Day 163 only at the study group level (ie, data will be provided with each group having a fake designation). For the final analysis, all parties will be unblinded to all data at the subject level at Day 142 (Groups A-D, G-J) and Day 262 (Groups E, F, K, L).

With the exception of the unblinded study staff who administer the IP and a separate unblinded monitor who will monitor IP accountability, all other study staff are to remain blinded until CSR database freeze and a formal unblinding is scheduled. The members of the IDMC will review subject level unblinded safety data on an ad hoc basis for any immediate concerns that are observed. A separate unblinded team will handle any ad hoc production of unblinded tables, listings, and figures for ad hoc IDMC meetings. Blinded individuals will not be made aware of any unblinded data provided to the IDMC.

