6.2.5.2 Solicited Local and Systemic Reactogenicity Symptoms

All subjects will record solicited local and systemic reactions and other unsolicited symptoms/complaints, including start and stop dates, on an 8-day diary card following each vaccination. The investigator or his/her designee will review the information from the diary card or from memory with the subject at each visit and grade reactogenicity using a standard toxicity grade (Appendix 3, Section 12.3). The diary card will be collected from the subjects and stored as a source document.

- Solicited local reactions at the injection site will include erythema/redness, induration/swelling, and pain.
- Solicited systemic reactions will include fever, myalgia, arthralgia, fatigue, headache, nausea, vomiting, diarrhea, and chills.

The above solicited local and systemic reactions will be recorded including start and stop dates, worst daily grade, any treatment required, and action taken. The investigator will assess if solicited local and systemic reactions will be considered as related to IP according to Section 6.2.5.6. The severity of local and systemic reactions will be graded using the FDA Toxicity Grading Scale for Healthy Adult and Adolescent Volunteers Enrolled in Preventive Vaccine Clinical Trials (Appendix 3, Section 12.3).

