Examine vaccination site ^r		Xs		Х	X ^s		X ^d		Xs		Х					Xď	Xt
AE/MAAE/PIMMC/ SAE assessment ^u		Х	Х	Х	X	Х	Х	Х	Х	Х	Х	Х	Х	Х	Х	Х	X

Table 12–2Schedule of Events, Groups E, F, K, L

Abbreviations: AE, adverse event; ALT, alanine aminotransferase; AST, aspartate aminotransferase; DC, diary card; eCRF, electronic case report form; EOS, end of study; ET, early termination; FDA, Food and Drug Administration; MAAE, medically attended adverse event; N/A, not applicable; PIMMC, potentially immune-mediated medical condition; SAE, serious adverse event; SUSAR, suspected unexpected serious adverse reaction; ULN, upper limit of normal; Unsch, unscheduled; V, visit; WOCBP, women of childbearing potential.

- ^a Telephone call assessment.
- ^b Prior to the completion of any study-related procedures.
- Vital sign measurements include oral temperature, pulse rate, and blood pressure. Vital signs will be measured before blood is collected, at both pre-vaccination and 30±5-minute postvaccination time points on a vaccination day. Diastolic and systolic blood pressure will be measured after the subject is seated for at least 5 minutes.
- ^d If clinically indicated.
- e Prior to vaccination.
- ^f Ask subject a standard nonleading question to elicit any medically related changes in their well-being. Ask if they have been hospitalized, had any accidents, used any new medications, received any vaccinations, or changed concomitant medication regimens (both prescription and over-the-counter medications).

Protocol: BP-I-16-005 Version 2.0

- 26 February 2018
- ^g Diary Card I (Days 1-8), III (Days 22-29), and V (Days 142-149) will be used to collect unsolicited and solicited local and systemic reactions. Diary Card II (Days 9-21), IV (Days 30-43), VI (Days 150-163) will be used to collect unsolicited AEs.
- ^h If applicable, according to the protocol period, collect and review DC with subject.
- ⁱ Use of all concomitant medications that the subject is taking at the time of Visit 1, medications taken up to 14 days prior to Visit 1, and vaccines received 12 months prior to Visit 1 will be recorded in the subject's eCRF.
- ^j Obtained by interview and by review of diary card completed by the subject.
- ^k Any physical examination findings will be collected in the eCRF for medical history data presentation.

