All AEs reported after the first dose of IP will be summarized in tables. AEs within 21 days of each dose of IP, and before the date and time of the next dose of IP (if applicable) will be summarized in tables based on each dose only (Dose 1, 2 for Groups A-D, G-J; Dose 1, 2, 3 for Group E, F, K and L). When the time of an AE is missing and the AE start date is on the date of vaccination, then that AE will be considered as happening after the corresponding dose of IP.

All AEs will be summarized by presenting the number and percentage of subjects having any AEs and having each individual adverse event based on SOC and PT, and PT only. At each level of subject summarization, a subject is counted once if the subject reported one or more events. Percentages will be calculated out of the number of subjects as treated per study group in the Safety Set. For the dose-specific AE summaries, percentages will be calculated out of the number of subjects as treated per study group corresponding to Dose 1, Dose 2 or Dose 3.

Unless otherwise stated, AEs will be sorted in descending order by frequency of SOC and PT.

The following summaries, based on Dose 1 only, Dose 2 only, and both Dose 1 and Dose 2 for Groups A-D, G-J and Dose 1 only, Dose 2 only, Dose 3 only, and all Dose 1, Dose 2 and Dose 3 for Groups E, F, K and L will be provided:

- Overview summary of the number and percentage of subjects with any AE, SAE, AE related to IP, AE leading to study withdrawal, AE leading to death, solicited local AE, severe solicited local AE, solicited systemic AE, severe solicited systemic AE, MAAE, PIMMC, unsolicited AE, severe unsolicited AE, and unsolicited AE related to IP
- All AEs by SOC and PT
- All AEs by AE Type and PT
- All AEs by SOC, PT and Severity

- All AEs by SOC, PT and Relationship
- All unsolicited AEs by SOC, PT and Day of Onset

The following summaries with 95% exact CIs using Clopper Pearson method, based on events recorded during the 8 days post each vaccination will be provided as the analysis of primary safety endpoint:

- Solicited Local AEs by Severity
- Solicited Systemic AEs by Severity

All MAAEs and PIMMCs after the first dose of IP will be summarized in a table by SOC, PT and Severity.

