9.2 Vaccination Site Examinations

The vaccination site examinations include pain, erythema/redness, induration/swelling, and other local symptoms at the site of injection and will be conducted 30 minutes and 8 days post each vaccination, ET if clinically indicated, and unscheduled visits (if the unscheduled visit occurs within 8 days post each vaccinations). The size of measurable erythema/redness and induration/swelling will be categorized as: <2.5 cm, 2.5 - 5 cm, 5.1 - 10 cm, and >10 cm. Vaccination site examination results will be classified according to the FDA Toxicity Grading Scale (See Appendix 3, Section 14.3, Grade 1 = Mild, Grade 2 = Moderate, Grade 3 = Severe, Grade 4 = Potentially Life Threatening) based on quantifiable criteria. The number and percentage of subjects who have vaccination site reactions involving pain, erythema/redness, induration/swelling, and other local symptoms will be summarized separately for each vaccination site reactions involving measurable redness and swelling will be summarized by size category. This summary will be performed on the Safety Set by treatment received according to first, second or third dose as appropriate.

All vaccination site examination results will be included in a data listing containing all subjectlevel data collected in the eCRF. All subjects with severe reaction based on injection site examination will be included in a data listing.

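### The Day 29 injection-site examination after dose 2 is routine in the eight 2-dose groups but conditional in the four 3-dose groups, contrary to SAP 9.2

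*Protocol*

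**What the plan says.** Visit 6 is Day 29 in every group, 7 days after the second dose (Day 8 when the vaccination day is counted). The row "Examine vaccination site" treats it differently in the two schedules. Protocol Table 12-1 (Groups A-D, G-J) has an unqualified mark. Protocol Table 12-2 (Groups E, F, K, L) attaches footnote d, "If clinically indicated". SAP Tables 14-1 and 14-2 repeat the difference.

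The SAP text makes no such distinction. Section 9.2 says that examinations "will be conducted 30 minutes and 8 days post each vaccination, ET if clinically indicated", so the conditional wording belongs to early termination and not to any scheduled visit. On the analysis it says: "This summary will be performed on the Safety Set by treatment received according to first, second or third dose as appropriate".

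Two other provisions bear on the point. Protocol 6.2.5.2 collects solicited reactions by diary card in every group: "All subjects will record solicited local and systemic reactions and other unsolicited symptoms/complaints". Protocol 5.5 exempts from the blind the staff member who prepares and administers the product and the accountability monitor, then states: "All other persons involved in the study will be blinded to study group assignment, including the study staff observing the subject after vaccination".

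**The concern.** A by-dose summary of site examinations is readable across groups only if the examination was sought in the same way in each group. Here the dose 2, Day 29 examination is sought from everyone in eight groups and only on indication in four.

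The four are not an arbitrary set. By Protocol Table 3-1, E, F, K and L are the only groups whose second dose repeats the first strain; A-D and G-J all switch strain. Routine versus conditional examination therefore coincides exactly with heterologous versus homologous second dose, a distinction named in the primary safety objective. Some columns would otherwise invite direct reading: F receives the same strain and adjuvant at dose 2 as A, B and C, and L the same as G, H and I.

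At stake are the staff-assessed Day 29 reaction rates after dose 2, the separate listing of severe reactions from the examination (SAP 9.2), and the site-examination listing that goes to the IDMC if a pausing rule is met (SAP 11.1).

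There is also a blinding question. Whoever decides at Day 29 whether the examination is mandatory must know whether the subject is in a 2-dose or a 3-dose series.

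**Working it through.** The plan gives no figure on this point to reproduce, so the check is a cell-by-cell reading followed by simple arithmetic.

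**1. The site-examination row, by visit**

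| Schedule | V1 (dose 1) | V3 (Day 8) | V4 (dose 2) | V6 (Day 29) | V8 (Day 142) | V10 (Day 149) |
|---|---|---|---|---|---|---|
| Table 12-1, Groups A-D, G-J | 30 min | routine | 30 min | routine | none | no visit |
| Table 12-2, Groups E, F, K, L | 30 min | routine | 30 min | if indicated | 30 min (dose 3) | routine |

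The SAP schedules give the same entries. Within Table 12-2, the 7-day examinations after doses 1 and 3 are routine, so Visit 6 is the only exception. The 30-minute examination after dose 2 is routine in both schedules.

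**2. Subjects affected** (60 per group, Protocol 7.4)

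- Conditional at Visit 6: 4 × 60 = 240 of 720, or 33.3%.
- Routine at Visit 6: 8 × 60 = 480.

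**3. Direction of bias**

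Let p be the true share of subjects with a site reaction at Day 29, s the share of reactors examined under the conditional rule, and f the share of non-reactors examined.

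- Safety Set denominator: observed rate = p·s.
- Examined-only denominator: observed rate = p·s / [p·s + (1 − p)·f].

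The documents give none of these three quantities. Assumed here: p from 5% to 20%, s from 25% to 75%, f = 5%. The last two columns show the range over s.

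| p | Reactors in 240 | Found by examination | Rate, Safety Set | Rate, examined only |
|---|---|---|---|---|
| 5% | 12 | 3 to 9 | 1.25% to 3.75% | 20.8% to 44.1% |
| 10% | 24 | 6 to 18 | 2.5% to 7.5% | 35.7% to 62.5% |
| 20% | 48 | 12 to 36 | 5% to 15% | 55.6% to 78.9% |

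For example, with p = 20% and s = 75%: 0.15 / (0.15 + 0.80 × 0.05) = 0.15 / 0.19 = 78.9%. One denominator understates the rate and the other overstates it. If every reactor is examined (s = 100%), the Safety Set rate equals p and there is no bias.

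**4. The cue to group**

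- Visits 1 to 8 fall on the same study days in both schedules, so the calendar does not reveal the series before dose 3 at Day 142. That is 142 − 29 = 113 days after Visit 6.
- Knowing which Visit 6 rule applies narrows 12 groups to 8 or 4. The chance of guessing the exact group rises from 1/12 = 8.3% to (8/12)(1/8) + (4/12)(1/4) = 1/6 = 16.7%.
- Adjuvant stays at 50%: the 2-dose schedule holds four AS03 and four MF59 groups, the 3-dose schedule two of each.

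**The case against.** The strongest reply is that little depends on this table. The study is descriptive, the SAP plans no formal between-group comparison for primary or secondary objectives, and the exploratory comparisons concern HAI titres and seroprotection only. Site examination is not among the listed endpoints. The primary safety analysis is "based on events recorded during the 8 days post each vaccination". The means of collecting those events after dose 2 are the same in both schedules: diary card III for Days 22-29, the measuring tool at Visit 4, and the Visit 6 interview and diary review. This stands and limits the weight of the point. It does not remove the contradiction, because SAP 9.2 still plans a by-dose summary of examinations.

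The mark may also be a drafting slip, given the routine examinations at Visits 3 and 10. That is plausible, but it stands in the current schedules of both documents, and sites would follow it.

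On blinding, it can be said that the cue shows series only, that Protocol 3.1 speaks of unique group assignment, and that no dummy third dose is planned, so the series becomes known at Day 142 anyway. The limits are right. But Protocol 5.5 is worded more broadly, and Day 29 is well before Day 142. It can also be said that staff who do not know the series cannot apply two rules, so ascertainment would not differ. True, but then the schedule cannot be followed as written.

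Three stronger readings are tempting and not supported:

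- A reader might infer that reaction rates in E, F, K and L would be grossly inflated, even to 100%. That needs an examined-only denominator, which SAP 9.2 does not state. If 20% react and exactly those are examined, a Safety Set denominator gives 48/240 = 20%, the true value.
- A reader might infer that dose 2 reactogenicity as a whole, or the primary safety endpoint, is compromised. The equal diary collection and the routine 30-minute examination do not support that.
- A reader might infer that the blind to adjuvant or exact group is lost. Both schedules contain both adjuvants and several groups.

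**Conclusion.** The inconsistency is real and narrow. The Visit 6 examination has one status in 480 subjects and another in about 240, and the conditional status contradicts SAP 9.2. The Day 29 staff-examination results after dose 2 would not be comparable between the 3-dose groups and the rest, and that division coincides with homologous versus heterologous second dose.

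The size of any bias cannot be fixed from the documents. Its direction turns on how unexamined subjects are counted, and the rates in the working rest on assumed reaction and examination frequencies. The count of 240 rests only on the planned 60 per group.

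The cue to 2-dose versus 3-dose series before Day 142 is a secondary consequence. The point deserves correction because it is specific and cheap to fix, not because it threatens the trial's main safety result.

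**What to change.** Reconcile Protocol Tables 12-1 and 12-2, SAP Tables 14-1 and 14-2, and SAP 9.2 so that the Visit 6 site examination has the same status in all 12 groups. That also removes the need for staff to know the series at Day 29.

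If any difference is kept, SAP 9.2 should:

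- state the denominator, including how subjects without an examination are counted;
- report the number examined per group;
- mark the dose 2, Day 29 results for E, F, K and L as not comparable with the other groups.

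There is no need to drop those four groups from the summary; the number examined lets a reader judge the data.

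The cost is small: the visit already takes place in every group, so the change is an edit to the Visit 6 cell in the affected tables plus, if needed, a few sentences in SAP 9.2. If some subjects have already passed Visit 6, the number examined should be reported in any case.

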12.2 Appendix 2: Potentially Immune-Mediated Medical Conditions

An adverse event of special interest (serious or nonserious) is one of scientific and medical concern specific to the sponsor's product or program, for which ongoing monitoring and rapid communication by the investigator to the sponsor can be appropriate. Such an event might warrant further investigation in order to characterize and understand it. Depending on the nature of the event, rapid communication by the trial sponsor to other parties (eg, regulators) might also be warranted (based on Council for International Organizations of Medical Sciences VI).

For this study, adverse events of special interest will include the following list of PIMMCs:

Gastrointestinal disorders

- Autoimmune pancreatitis
- Celiac disease
- Crohn's disease
- Microscopic colitis
- Ulcerative colitis
- Ulcerative proctitis

Liver disorders

- Autoimmune cholangitis
- Autoimmune hepatitis
- Primary biliary cirrhosis
- Primary sclerosing cholangitis

Metabolic diseases

- Addison's disease
- Autoimmune hypophysitis
- Autoimmune thyroiditis (including Hashimoto thyroiditis)
- Diabetes mellitus type I

H5 Influenza Vaccine With Either AS03 or MF59

26 February 2018

Protocol: BP-I-16-005 Version 2.0

• Grave's or Basedow's disease

Musculoskeletal disorders

- Antisynthetase syndrome
- Dermatomyositis
- Juvenile chronic arthritis (including Still's disease)
- Mixed connective tissue disorder
- Polymyalgia rheumatic
- Polymyositis
- Psoriatic arthropathy
- Relapsing polychondritis
- Rheumatoid arthritis
- Scleroderma, including diffuse systemic form and CREST syndrome
- Spondyloarthritis, including ankylosing spondylitis, reactive arthritis (Reiter's Syndrome), and undifferentiated spondyloarthritis
- Systemic lupus erythematosus
- Systemic sclerosis

Neuroinflammatory disorders

- Acute disseminated encephalomyelitis, including site-specific variants (eg, noninfectious encephalitis, encephalomyelitis, myelitis, radiculomyelitis)
- Cranial nerve disorders, including paralyses/paresis (eg, Bell's palsy)
- Guillain-Barré syndrome, including Miller Fisher syndrome and other variants
- Immune-mediated peripheral neuropathies and plexopathies, including chronic inflammatory demyelinating polyneuropathy, multifocal motor neuropathy and polyneuropathies associated with monoclonal gammopathy
- Multiple sclerosis
- Narcolepsy

H5 Influenza Vaccine With Either AS03 or MF59

26 February 2018

Protocol: BP-I-16-005 Version 2.0

- Optic neuritis
- Transverse myelitis
- Myasthenia gravis, including Eaton-Lambert syndrome

Skin disorders

- Alopecia areata
- Autoimmune bullous skin diseases, including pemphigus, pemphigoid and dermatitis herpetiformis
- Cutaneous lupus erythematosus
- Erythema nodosum
- Morphoea
- Lichen planus
- Psoriasis
- Sweet's syndrome
- Vitiligo

Vasculitides

- Large vessels vasculitis including: giant cell arteritis such as Takayasu's arteritis and temporal arteritis
- Medium sized and/or small vessels vasculitis including the following: polyarteritis nodosa, Kawasaki's disease, microscopic polyangiitis, Wegener's granulomatosis, Churg– Strauss syndrome (allergic granulomatous angiitis), Buerger's disease thromboangiitis obliterans, necrotizing vasculitis and antineutrophil cytoplasmic antibody (ANCA) positive vasculitis (type unspecified), Henoch-Schonlein purpura, Behcet's syndrome, leukocytoclastic vasculitis

Others

- Antiphospholipid syndrome
- Autoimmune hemolytic anemia

•

26 February 2018

Protocol: BP-I-16-005 Version 2.0

- Autoimmune glomerulonephritis (including IgA nephropathy, glomerulonephritis rapidly progressive, membranous glomerulonephritis, membranoproliferative glomerulonephritis, and mesangioproliferative glomerulonephritis)
- Autoimmune myocarditis/cardiomyopathy
- Autoimmune neutropenia
- Autoimmune pancytopenia
- Autoimmune thrombocytopenia
- Goodpasture syndrome
- Idiopathic pulmonary fibrosis
- Pernicious anemia
- Polyglandular autoimmune syndrome
- Raynaud's phenomenon
- Sarcoidosis
- Sjögren's syndrome
- Stevens-Johnson syndrome
- Uveitis

12.3 Appendix 3: US FDA Guidance for Industry: Toxicity Grading Scale for Healthy Adult and Adolescent Volunteers Enrolled in Preventive Vaccine Clinical Trials (a partial list)

http://www.fda.gov/downloads/BiologicsBloodVaccines/GuidanceComplianceRegulatoryInf ormation/Guidances/Vaccines/ucm091977.pdf

H5 Influenza Vaccine With Either AS03 or MF59

Protocol: BP-I-16-005 Version 2.0

26 February 2018

Local Reaction to Injectable Product	Mild (Grade 1)	Moderate (Grade 2)	Severe (Grade 3)	Potentially Life Threatening (Grade 4)
Pain	Does not interfere with activity	Repeated use of non-narcotic pain reliever >24 hours or interferes with activity	Any use of narcotic pain reliever or prevents daily activity	Emergency room visit or hospitalization
Erythema/redness ^a	2.5-5 cm	5.1-10 cm	>10 cm	Necrosis or exfoliative dermatitis
Induration/swelling ^b	2.5-5 cm and does not interfere with activity	5.1-10 cm or interferes with activity	>10 cm or prevents daily activity	Necrosis

^a In addition to grading the measured local reaction at the greatest single diameter, the measurement should be recorded as a continuous variable.

^b Induration/swelling should be evaluated and graded using the functional scale as well as the actual measurement.

Vital Signs ^a	Mild (Grade 1)	Moderate (Grade 2)	Severe (Grade 3)	Potentially Life Threatening (Grade 4)
Fever (°C) ^b	38.0-38.4	38.5-38.9	39.0-40	>40
(°F) ^b	100.4-101.1	101.2-102.0	102.1-104	>104
Tachycardia – beats per minute	101-115	116-130	>130	ER visit or hospitalization for arrhythmia
Bradycardia – beats per minute ^c	50-54	45-49	<45	ER visit or hospitalization for arrhythmia
Hypertension (systolic) – mm Hg	141-150	151-155	>155	ER visit or hospitalization for malignant hypertension
Hypertension (diastolic) – mm Hg	91-95	96-100	>100	ER visit or hospitalization for malignant hypertension
Hypotension (systolic) – mm Hg	85-89	80-84	<80	ER visit or hospitalization for hypotensive shock
Respiratory rate – breaths per minute	17-20	21-25	>25	Intubation

Abbreviation: ER, emergency room.

^a Subject should be at rest for all vital sign measurements.

^b Oral temperature; no recent hot or cold beverages or smoking.

^c When resting heart rate is between 60 to 100 beats per minute. Use clinical judgement when characterizing bradycardia among some healthy subject populations, for example, conditioned athletes.

H5 Influenza Vaccine With Either AS03 or MF59

Protocol: BP-I-16-00	5 Version 2.0			26 February 2018
Systemic (General)	Mild (Grade 1)	Moderate (Grade 2)	Severe (Grade 3)	Potentially Life Threatening (Grade 4)
Fever (°C) ^a	38.0-38.4	38.5-38.9	39.0-40	>40
(°F) ^a	100.4-101.1	101.2-102.0	102.1-104	>104
Chills ^b	Symptoms causing no or minimal interference with usual social and functional activities	Symptoms causing greater than minimal interference with usual and social functional activities	Symptoms causing inability to perform usual social and functional activities	Not applicable
Arthralgia ^b	Joint pain causing no or minimal interference with usual and social functional activities	Joint pain causing greater than minimal interference with usual and social functional activities	Joint pain causing inability to perform usual and social and functional activities	Disabling joint pain causing inability to perform basic self-care functions
Nausea/vomiting	No interference with activity or 1-2 episodes/24 hours	Some interference with activity or >2 episodes/24 hours	Prevents daily activity, requires outpatient IV hydration	ER visit or hospitalization for hypotensive shock
Diarrhea	2-3 loose stools or <400 g/24 hours	4-5 loose stools or 400-800 g/24 hours	6 or more watery stools or 800 g/24 hours or requires outpatient IV hydration	ER visit or hospitalization
Headache	No interference with activity	Repeated use of non-narcotic pain reliever >24 hours or some interference with activity	Significant; any use of narcotic pain reliever or prevents daily activity	ER visit or hospitalization
Fatigue	No interference with daily activity	Some interference with daily activity	Significant; prevents daily activity	ER visit or hospitalization
Myalgia	No interference with activity	Some interference with activity	Significant; prevents daily activity	ER visit or hospitalization
Illness or clinical adverse event (as defined according to applicable regulations)	No interference with activity	Some interference with activity not requiring medical intervention	Prevents daily activity and requires medical intervention	ER visit or hospitalization

Abbreviations: ER, emergency room; IV intravenous.

а Oral temperature; no recent hot or cold beverages or smoking. (Note, this same information is also provided in Vital Signs table above.)

b Definition from Department of Health and Human Services, National Institutes of Health, National Institute of Allergy and Infectious Diseases (US). Division of AIDS (DAIDS) Table for Grading the Severity of Adult and Pediatric Adverse Events. Version 2.1, July 2017 [35 screens]. Available from http://rsc.tech-res.com/docs/defaultsource/safety/division-of-aids-(daids)-table-for-grading-the-severity-of-adult-and-pediatric-adverse-events-corrected-v-2-1.pdf?sfvrsn=2.

H5 Influenza Vaccine With Either AS03 or MF59

Protocol: BP-I-16-005 Vers	Protocol: BP-I-16-005 Version 2.0								
Serum ^a	Mild (Grade 1)	Moderate (Grade 2)	Severe (Grade 3)	Potentially Life Threatening (Grade 4) ^b					
Blood urea nitrogen mg/dL	23-26	27-31	>31	Requires dialysis					
Creatinine mg/dL	1.5-1.7	1.8-2.0	2.1-2.5	>2.5 or requires dialysis					
Liver function tests – ALT, AST increase by factor	1.1 -2 .5 × ULN	2.6-5.0 × ULN	5.1-10 × ULN	$>10 \times ULN$					
Bilirubin – when accompanied by any increase in liver function test increase by factor	1.1-1.25 × ULN	1.26-1.5 × ULN	1.51-1.75 × ULN	>1.75 × ULN					
Bilirubin – when liver function test is normal; increase by factor	1.1-1.5 × ULN	1.6-2.0 × ULN	2.0-3.0 × ULN	>3.0 × ULN					

Abbreviations: ALT, alanine aminotransferase; AST, aspartate aminotransferase; ULN, upper limit of normal.

a The laboratory values provided in the tables serve as guidelines and are dependent upon institutional normal parameters. Institutional normal reference ranges should be provided to demonstrate that they are appropriate.

b The clinical signs or symptoms associated with laboratory abnormalities might result in characterization of the laboratory abnormalities as Potentially Life Threatening (Grade 4).

H5 Influenza Vaccine With Either AS03 or MF59

Protocol: BP-I-16-005 Version 2.0

26 February 2018

	51011 2.0			201 c ordary 201
Hematology ^a	Mild (Grade 1)	Moderate (Grade 2)	Severe (Grade 3)	Potentially Life Threatening (Grade 4)
Hemoglobin (female) – g/dL	11.0-12.0	9.5-10.9	8.0-9.4	<8.0
Hemoglobin (female) change from baseline value - g/dL	Any decrease – 1.5	1.6-2.0	2.1-5.0	>5.0
Hemoglobin (male) – g/dL	12.5-13.5	10.5-12.4	8.5-10.4	<8.5
Hemoglobin (male) change from baseline value – g/dL	Any decrease – 1.5	1.6-2.0	2.1-5.0	>5.0
WBC increase - cell/mm ³	10 800-15 000	15 001-20 000	20 001-25 000	>25 000
WBC decrease - cell/mm ³	2 500-3 500	1 500-2 499	1 000-1 499	<1 000
Lymphocytes decrease – cell/mm ³	750-1 000	500-749	250-499	<250
Neutrophils decrease – cell/mm ³	1 500-2 000	1 000-1 499	500-999	<500
Eosinophils – cell/mm ³	650-1 500	1501-5 000	>5 000	Hypereosinophilic
Platelets decrease – cell/mm ³	125 000-140 000	100 000-124 000	25 000-99 000	<25 000
PT – increase by factor	$1.0\text{-}1.10\times ULN^b$	$1.11-1.20 \times ULN$	1.21-1.25 × ULN	>1.25 ULN
PTT – increase by factor	$1.0-1.2 \times ULN$	1.21-1.4 × ULN	1.41-1.5 × ULN	>1.5 ULN

Abbreviations: PPT, partial thromboplastin time; PT, prothrombin time; ULN, upper limit of normal; WBC, white blood cell.

^a The laboratory values provided in the tables serve as guidelines and are dependent upon institutional normal parameters. Institutional normal reference ranges should be provided to demonstrate that they are appropriate.

^b ULN is the upper limit of the normal range.

